5.2.1 Starting Dose and Dose Modifications of Protocol-Specified Treatment

The starting dose in this study will be 600mg rucaparib PO (per os) BID (twice daily).

5.2.2 Dose Modification Criteria

The dose of rucaparib should be held if any of the following are observed and a dose reduction should be considered or implemented:

- Grade 3 or 4 hematologic toxicity
- Grade 3 or 4 non-hematologic toxicity (except for alopecia, nausea, vomiting, or diarrhea adequately controlled with systemic antiemetic/antidiarrheal medication administered in standard doses according to the study center routines)
- In addition, and at the discretion of the investigator, the dose of rucaparib may be held and/or reduced for Grade 2 toxicity not adequately controlled by concomitant medications and/or supportive care.

Treatment delays and modifications may be made at the discretion of the treating physician in the interest of patient safety

Treatment with rucaparib should be held until the toxicity resolves to \leq CTCAE Grade 2. BID dosing may then be resumed at either the same dose or a lower dose, per investigator discretion. If treatment is resumed at the same dose, and the patient experiences the same toxicity, the dose should be reduced following resolution of the event to \leq CTCAE Grade 2. If the patient continues to experience toxicity, additional dose reduction steps are permitted. If a patient continues to experience toxicity despite multiple dose reduction steps, treatment may be discontinued, upon the investigator's discretion.

Dose reduction steps are presented in Table 5.2.2.

Dose re-escalation upon resolution of toxicity to \leq CTCAE Grade 1 is permitted, upon the investigator's discretion.

Management of Rucaparib Treatment-Emergent ALT/AST Elevations

- Grade 4 ALT/AST elevations: hold rucaparib until values have returned to Grade 2 or better, then resume rucaparib with a dose reduction. Monitor liver function tests weekly for 3 weeks after rucaparib has been restarted.
- Grade 3 ALT/AST elevations should be managed as follows:
 - Monitor liver function tests weekly until resolution to \leq Grade 2.
 - Continuation of rucaparib with elevation of ALT/AST up to Grade 3 is permitted provided bilirubin is $<$ ULN, alkaline phosphatase is $<$ 3 x ULN, and there are no other signs of liver dysfunction.

If patient has Grade 3 ALT/AST and continues on rucaparib, and levels do not decline within 2 weeks or they continue to rise, treatment interruption and resolution to \leq Grade 2 will be required before rucaparib can be resumed, either at the current dose or at a reduced dose

Table 5.2.2 Rucaparib Dose Reduction Steps

TABLE 5.2.2

CONFIDENTIAL

This material is the property of the University of Pennsylvania.

Tablets	300/ 200mg
Starting Dose	600 mg BID
Dose Level -1	500 mg BID
Dose Level -2	400 mg BID
Dose Level -3*	300 mg BID
* Consult with medical monitor before reducing to this dose	

Management of anemia including: evaluation for MDS/AML and follow-up of patients who discontinue treatment with ongoing anemia.'

- If the patient develops anemia CTCAE Grade ≥ 3 , rucaparib treatment should be held until the anemia resolves to CTCAE Grade ≤ 2 whereupon daily dosing may then be resumed at either the same dose or a lower dose, per investigator discretion.
- If the duration of dosing is interrupted for > 14 consecutive days due to anemia CTCAE Grade ≥ 3 , treatment should be permanently discontinued, unless otherwise agreed between the investigator and the Principal Investigator
- In addition, if anemia CTCAE Grade ≥ 3 persists for > 14 consecutive days, or a dependence upon blood transfusion occurs, then weekly complete blood counts should be performed until resolution of the event.
- If, after 42 days of interruption of rucaparib, the anemia has not recovered to CTCAE Grade ≤ 1 then the patient should be referred to a hematologist and analysis of the bone marrow with cytogenetic studies are recommended according to standard hematologic practice.
- The bone marrow analysis should include a bone marrow aspirate (for cellular morphology, cytogenetic analysis, and flow cytometry) and a core biopsy (for bone marrow cellularity).

5.2.3 Criteria for Re-Treatment

A new cycle of treatment may begin if:

- ANC $\geq 1.0 \times 10^9/L$
- Platelet count $\geq 100 \times 10^9/L$
- Non-hematologic toxicities have returned to baseline or \leq CTCAE Grade 1 severity (or, at the investigator's discretion, \leq CTCAE Grade 2 severity if not considered a safety risk for the patient)
- Elevations in AST/ALT requiring a dose hold: Rucaparib may be restarted once AST/ALT return \leq CTCAE Grade 2 severity provided LFTs are measured weekly for 3 weeks following restarting rucaparib.

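### Sections 5.2.2 and 5.2.3 set conflicting conditions for dosing at the start of a cycle, and the protocol states neither the scope of each nor which prevails

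*Combined protocol and SAP*

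**What the plan says.** Section 5.2 has patients take rucaparib twice daily in continuous 28-day cycles, with no rest period.

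Section 5.2.2 of the protocol lists the triggers for a hold. For blood counts the trigger is "Grade 3 or 4 hematologic toxicity". For other toxicity it is again Grade 3 or 4, but nausea, vomiting and diarrhea that are adequately controlled by medication are excepted. The general restart rule is "Treatment with rucaparib should be held until the toxicity resolves to" CTCAE Grade 2 or lower, after which "BID dosing may then be resumed at either the same dose or a lower dose, per investigator discretion". A separate paragraph allows dosing to continue with Grade 3 ALT/AST if bilirubin, alkaline phosphatase and other signs of liver function meet stated conditions. The anemia rules after Table 5.2.2 require a hold at Grade 3 or higher until Grade 2 or lower, "whereupon daily dosing may then be resumed at either the same dose or a lower dose, per investigator discretion".

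Section 5.2.3 is headed as criteria for re-treatment and begins "A new cycle of treatment may begin if". Its list is ANC of at least 1.0 x 10^9/L; platelets of at least 100 x 10^9/L; "Non-hematologic toxicities have returned to baseline or" Grade 1 or lower, with Grade 2 at the investigator's discretion if not thought a safety risk; and, for AST/ALT elevations that required a hold, Grade 2 or lower with weekly liver tests for three weeks after restart. Hemoglobin is not listed.

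The visit instructions in 6.3.1 (Cycles 1 and 2) and 6.1.3 (Cycles 3 and beyond) refer re-treatment and dose modification to the protocol's criteria without naming a section.

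**The concern.** With continuous dosing, each Day 1 is a dosing decision to which both sections apply. Nor is 5.2.3 confined to patients who were never held: its heading and its AST/ALT item both concern treatment after an interruption. If the two lists disagree, the same laboratory result or toxicity can mean dosing under one section and no dosing under the other.

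Two things are at stake. The rules govern whether a patient with low counts or Grade 3 toxicity takes the drug, so an ambiguity in them is a safety matter. The incidence of dose modifications is also a secondary endpoint (3.2.2 and 8.2), and the number of holds and delays recorded would partly reflect which section the treating investigator applied.

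**Working it through.** The plan gives no figure to reproduce. The check sets the two sections side by side, item by item.

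| Finding | 5.2.2 | 5.2.3, to begin a cycle | Same answer? |
|---|---|---|---|
| Platelets | Hold at Grade 3-4; may resume at Grade 2 or lower | At least 100 x 10^9/L, no discretion | No, unless the Grade 2 floor is 100 |
| ANC | Same general rule | At least 1.0 x 10^9/L, no discretion | Yes, if the Grade 2 floor is 1.0 |
| Hemoglobin | Hold at Grade 3 or higher; may resume at Grade 2 or lower | Not listed | Omission; no competing instruction |
| Grade 2 non-hematologic toxicity | May resume | Baseline or Grade 1; Grade 2 by discretion | Largely |
| Grade 3-4 nausea, vomiting or diarrhea, adequately controlled | No hold required | Not exempt from the grade limit | No |
| Grade 3 ALT/AST, conditions met, no hold | Dosing may continue | Not exempt; the AST/ALT item covers only elevations that required a hold | No |
| ALT/AST after a hold | Grade 2 or lower | Grade 2 or lower | Yes |

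**Platelets.** The protocol cites CTCAE v4.03 but prints no cut-offs, so let L x 10^9/L be the lower limit of Grade 2. A count is acceptable to 5.2.2 if it is at least L and to 5.2.3 if it is at least 100. The counts in dispute run from L to below 100, a band of width 100 - L:

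- L = 50: 100 - 50 = 50, counts 50-99
- L = 75: 100 - 75 = 25, counts 75-99
- L = 100: 100 - 100 = 0, no conflict

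Take a count of 90 with L at or below 90. In a patient whose hold spans a Day 1, 5.2.2 permits restart and 5.2.3 does not permit the cycle to begin. In a patient never held, 5.2.2 triggers no hold and the continuous schedule carries on, while 5.2.3 again bars the new cycle. The same count on Day 15 of Cycle 1 or 2, when hematology is also drawn (6.1), requires no action.

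Such counts are foreseeable. Entry requires platelets only above 100 x 10^9/L (4.1). Section 1.4.1 lists thrombocytopenia among treatment-related events reported in at least 15% of patients at 600 mg BID and says that myelosuppression may be delayed.

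**Timing in later cycles.** Footnotes x and y to the schedule allow 56-day and then 84-day cycles with monthly counts. Taking a month as 28 days, 56/28 = 2 and 84/28 = 3, so only one count in two, and then one in three, falls at a cycle start where 5.2.3 literally applies.

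**Toxicities that 5.2.2 lets a patient be dosed through.** A patient with Grade 3 ALT/AST who meets the conditions, or with controlled Grade 3 nausea, may continue under 5.2.2. At the next Day 1, 5.2.3 asks for baseline or Grade 1, or Grade 2 by discretion. Unless Grade 3 was already the baseline, the patient fails, and the discretion clause stops at Grade 2.

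**A smaller point inside 5.2.2.** It also says that "the dose of rucaparib may be held and/or reduced for Grade 2 toxicity not adequately controlled by concomitant medications and/or supportive care". The general restart condition is Grade 2 or lower, which such a patient already meets when the hold begins.

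**The case against.** The strongest reply is that the sections answer different questions and can be applied together. Section 5.2.2 says when dosing may resume after a hold; 5.2.3 adds a check at the start of a cycle. Both are worded as permissions, so satisfying both is possible, and an extra check is not in itself a contradiction. The treating physician may also delay treatment for safety under 5.2.2, and an independent medical monitor takes part in dose-modification decisions (9.14).

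That reading is coherent, but the protocol does not state it. It would also mean that the ALT/AST and controlled nausea, vomiting or diarrhea provisions of 5.2.2 lapse at the next Day 1, however soon that falls, and nothing suggests this was intended. The power to delay does not relax the platelet threshold.

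Other parts of the reply stand:

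- **Anemia.** A reader might infer that a patient with Grade 3 anemia may begin a cycle because 5.2.3 omits hemoglobin. The documents do not support this. The hematologic trigger and the anemia rules in 5.2.2 require the hold on any day, and 5.2.3 does not override them.
- **Grade 2 non-hematologic toxicity.** A reader might see opposite rules here. The defaults differ, but the discretion clause in 5.2.3 largely closes the gap.
- **Grade 2 holds.** Both the hold and the restart are discretionary, so nothing forces an immediate restart.
- **Site differences.** The study has one center (Study Summary, 4.4), so any divergence would be between treating investigators or occasions, not sites.

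**Conclusion.** The point holds for two items. On platelets, counts from L to below 100 x 10^9/L are treated differently: 50-99 if L = 50, 75-99 if L = 75, none if L = 100. The size of the band rests on a grade limit that the documents do not print. On non-hematologic toxicity, Grade 3 ALT/AST under the stated conditions and adequately controlled Grade 3-4 nausea, vomiting or diarrhea may be dosed through under 5.2.2 but have no exemption in 5.2.3; this conflict needs no assumption about cut-offs. Both rest on reading 5.2.3 as a requirement at each Day 1, which is the evident purpose of such a list.

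The hemoglobin omission and the Grade 2 restart condition are minor related points. AST/ALT restart after a hold agrees between the sections, and ANC agrees if its Grade 2 floor is 1.0.

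A reader might go further and infer a distortion of PFS6. One week without drug is 7/183 = 3.8% of a six-month period taken as 183 days, but that is exposure arithmetic only. The documents do not give the number of patients who would be affected or any relation between a short hold and progression, so no effect on PFS6 can be claimed.

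**What to change.** Reconcile 5.2.2, including the ALT/AST and anemia rules, with 5.2.3 so that they do not give different answers for the same finding. State when each section applies (start of a cycle, restart after a hold, or both) and which prevails if they differ. In the same revision, clarify how 5.2.3 relates to the anemia rules and what ends a discretionary Grade 2 hold. Have the visit instructions in 6.3.1 and 6.1.3 cite the governing section. Which thresholds and rules stand is for the sponsor-investigator to decide.

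The cost is a wording amendment, with no added tests, visits or patients. The downside is that treating investigators may have to change current practice.

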5.2.4 Treatment Beyond Progression

If the patient has met criteria for radiologic progression by RECIST v1.1, but the patient is still receiving benefit from rucaparib (e.g., patient has mixed radiologic response or is continuing to have symptomatic benefit without decline in performance status) according to the Investigator, then continuation of treatment will be considered. In such cases, the decision to continue will be made by the Investigator, and must be documented prior to continuing treatment with rucaparib. Patients will continue to have all protocol-required assessments specified in the Schedule of Assessments Table.

CONFIDENTIAL

This material is the property of the University of Pennsylvania.

5.3 Prior and Concomitant Therapies

Patients who have received prior treatment with PARP inhibitor are not eligible to participate in this study. Patients who have demonstrated resistance to platinum agents (e.g. oxaliplatin, cisplatin) are not eligible to participate in this study.

During the study, supportive care (e.g. antiemetics; analgesics of pain control) may be used at the investigator's discretion and in accordance with institutional procedures.

All procedures performed (e.g., thoracentesis, paracentesis etc) and medications used during the study must be documented on the electronic case report form (eCRF).

5.3.1 Anticancer or Experimental Therapy

No other concomitant therapies for pancreatic cancer (including chemotherapy, radiation, hormonal treatment, antibody or other immunotherapy, gene therapy, vaccine therapy, angiogenesis inhibitors, or other experimental drugs) of any kind will be permitted while the patient is participating in the study with the exception of palliative radiation or gamma knife which may be allowed in discussion with the PI and Medical Monitor. Ongoing therapies for previously treated non-pancreatic cancer (e.g., hormonal treatment for prior breast cancer) are permitted.

5.3.2 Hematopoietic Growth Factors and Blood Products

Erythropoietin, darbepoetin alfa, and/or hematopoietic colony-stimulating factors for treatment of cytopenias should be administered according to institutional guidelines. Transfusion thresholds for blood product support will be in accordance with institutional guidelines.

5.3.3 CYP450 Isoenzyme Inhibitors, Inducers, and Substrates

Based on results of *in vitro* CYP interaction studies, caution should be used for concomitant medications with narrow therapeutic windows that are substrates of CYP2C19, CYP2C9, and/or CYP3A. Selection of an alternative concomitant medication is recommended.

Table 5.3.3 Examples of CYP Substrates with Narrow Therapeutic Range

CYP Enzyme	Substrates with Narrow Therapeutic Range ^a
CYP2C9	Warfarin, phenytoin
CYP2C19	S-mephenytoin
CYP3A	Alfentanil, astemizole, cisapride, cyclosporine, dihydroergotamine, ergotamine, fentanyl, pimozide, quinidine, sirolimus, tacrolimus, terfenadine

^aThe table is based on the Draft FDA Guidance on Drug Interaction Studies — Study Design, Data Analysis, Implications for Dosing, and Labeling Recommendations, 2012[38].

CYP substrates with narrow therapeutic range refers to drugs whose exposure-response relationship indicates that small increases in their exposure levels by the concomitant use of CYP inhibitors may lead to serious safety concerns (eg, Torsades de Pointes).

5.3.4 Bisphosphonates

Bisphosphonates are permitted.

5.3.5 Anticoagulants

Caution should be exercised in patients receiving oral rucaparib and concomitant warfarin as rucaparib showed a mixed inhibition of CYP2C9 *in vitro*. If appropriate, low molecular weight heparin should be considered as an alternative treatment. Patients taking warfarin should have international normalized ratio (INR) monitored regularly per standard clinical practice.

CONFIDENTIAL

5.3.6 Other Concomitant Medications

Therapies considered necessary for the patient's well-being may be given at the discretion of the investigator. Other concomitant medications, except for analgesics, chronic treatments for concomitant medical conditions, or agents required for life-threatening medical problems, should be avoided. Herbal and complementary therapies should not be encouraged because of unknown side effects and potential drug interactions.

In vitro data showed that rucaparib is an inhibitor of P-gp and thus patients taking digoxin, a P-gp substrate, should have their digoxin levels monitored regularly via standard clinical practice. Caution should also be exercised for concomitant use of certain statin drugs (eg, rosuvastatin and fluvastatin) due to potential increase in exposure from inhibition of BCRP and CYP2C9. All concomitant medications taken by the patient should be documented appropriately on the eCRF.

5.4 Receipt

Rucaparib will be received to our Perelman Center for Advanced Medicine Pharmacy and will be stored with no special storage conditions, ambient as per standard pharmacy practice

5.5 Storage

All tablets should be maintained in high-density polyethylene (HDPE) bottles with child-resistant caps and should be stored in the provided containers with no special storage conditions, ambient.

5.6 Preparation and Packaging

All tablets are provided in high-density polyethylene (HDPE) bottles with child-resistant caps and should be stored in the provided containers with no special storage conditions, ambient. Patients will be dispensed one or more strengths depending on their current dose of rucaparib. The number of bottles of each strength dispensed will be sufficient to supply 28 days treatment per cycle, including a small overage.

Study drug containers containing rucaparib tablets will be labeled according to national regulations for investigational products

5.7 Administration and Accountability

The investigator or designee will be responsible for distributing rucaparib to patients.

All patients will ingest rucaparib twice a day. Patients may take rucaparib on an empty stomach or with food. Each dose should be taken with at least 8 oz (240mL) of room temperature water. Tablets should be swallowed whole.

Patients should take rucaparib doses as close to 12 hours apart as possible, preferably at the same times every day. If a patient misses a dose (ie does not take it within 4 hours of the scheduled time), they should skip the missed dose and resume taking rucaparib with their next scheduled dose. Missed or vomited doses should not be made up.

A sufficient number of tablets will be provided to the patient to last until the next scheduled visit. Patients will be instructed to record daily doses taken or not taken in a dosing diary, and will be instructed to bring their rucaparib tablets, all containers (empty, partially used and/or unopened) and dosing diary to the next scheduled visit for reconciliation by site personnel.

5.8 Subject Compliance Monitoring

Documentation of dosing will be recorded in a study specific dosing diary. Study site personnel will review dosing information with the patient (or legally authorized representative) on scheduled clinic visit days, providing instructions regarding dose, dose frequency and the number of tablets to be taken for each dose.

CONFIDENTIAL

Patients (or legally authorized representative) will be instructed to record dosing information for rucaparib taken at home in the dosing diary and to bring the dosing diary and all unused tablets with them to scheduled clinic visits. A compliance check and tablet count will be performed by study personnel during clinic visits. Every effort should be made to ensure patients complete the dosing diary and return their study drug containers at the end of each cycle of treatment.

5.9 Return or Destruction of Investigational Product

Upon completion or termination of the study, all unused and/or partially used investigational product will be destroyed on-site in accordance with standard policies for the destruction of investigational agents.

6 STUDY PROCEDURES

6.1 Schedule of Assessment

All procedures and assessments are to be completed within ± 3 days of the scheduled time point.

Schedule of Assessments						
Procedure ^a	Screening Phase	Treatment Phase			Post-Treatment Phase	
	Day -28 to Day -1 (unless otherwise specified)	Cycles 1 & 2		Cycles 3+ ^{x & y}		
		Day 1 ^b	Day 15	Day 1	End of Treatment	28-day FU (28 \pm 3 days after last dose)
Informed Consent	X					
Demographics and Med/Onc History ^c	X					
Physical Exam, Height ^d , Weight	X	X		X	X	
Vital Signs ^f	X	X ^e		X ^e	X	
Adverse Events	X	X	X	X	X	X
Prior/Concomitant Medications and Procedures	X	X	X	X	X	
12-lead-ECG ^g	X				X	
Hematology ^h	X ⁱ	X	X	X ^x	X	
Serum Chemistry ^j	X ⁱ	X	X	X	X	
CA 19-9 measurement		X		X	X	
Coags if undergoing a tumor biopsy ^u	X				X	
Serum/Urine Pregnancy Test ^k (WOCBP only)	X	X		X	X	
Urinalysis ^l	X					
Disease Assessment/Tumor Scans ^m	X			X ⁿ	(X) ^o	(X) ^p
	Screening Phase	Treatment Phase				
	Day -28 to Day -1 (unless otherwise specified)	Cycles 1 & 2		Cycles 3+ x & y		
		Day 1	Day 15	Day 1		
Archival Tumor Tissue (if available)		X				
Tumor Tissue Biopsy (if safe/feasible) ^r	X				X ^w	
Research sample ^t		X		X	X	

CONFIDENTIAL

Schedule of Assessments							
Rucaparib Dispensation, Administration, Accountability		X		X	X		
Survival Status							X ^s

ALP = alkaline phosphatase, ALT = alanine transaminase, ANC = absolute neutrophil count, AST = aspartate transaminase, BUN = blood urea nitrogen, CR = complete response, CT = computed tomography, ECG = electrocardiogram, hrs = hours, MRI = magnetic resonance imaging, PET = positron emission tomography, PK = pharmacokinetics, PR = partial response, SAE = serious adverse event, WBC = white blood cell, WOCBP = women of childbearing potential

^a = Treatment cycles are 28 days except for patients who reach C11D1 and are clinically stable as per the investigator may be extended to a 56-day cycle. Unless otherwise specified, all assessments are to be completed within ± 3 days of scheduled time point. Delay of treatment schedule up to 10 days, as allowed by the protocol, is permitted at the discretion of the treating Investigator with approval of the PI (e.g. toxicity, weather, vacation). In addition, on a case by case basis the cycle length maybe extended to allow for planned vacations or emergency situations if deemed clinically stable by the PI.

^b = Any procedures required on Day 1 of Cycle 1 may be omitted if completed ≤ 3 days earlier during the screening period.

^c = Patient's medical record must include prior treatments received, dates of administration, date of progression, and radiology and/or medical report(s) to support assessment of disease progression, and, if applicable, intolerable toxicity to chemotherapy. Detailed BRCA1/2 test results are also required prior to enrollment.

^d = Height at screening only.

^e = Vital signs (blood pressure, pulse, and temperature) to be taken pre-dose on clinic visit days.

^f = AEs are recorded from the time of signing informed consent through 28 days after last dose of rucaparib. Ongoing SAEs will be followed to resolution or until SAE stabilizes.

^g = Heart rate, PR, QRS, QT, QTc and rhythm. Investigator to review results and assess as normal or abnormal (clinically significant or not clinically significant). ECGs to be repeated as clinically indicated.

^h = Includes CBC with differential which includes: hemoglobin, hematocrit, WBC and differential (with ANC) and platelet count. Blood will be analyzed by a local laboratory.

ⁱ = to be performed ≤ 7 days prior to the first dose of rucaparib.

^j = includes total protein, albumin, creatinine or estimated GFR using Cockcroft Gault formula, BUN, total bilirubin, ALP, ALT, AST, glucose, sodium, potassium, chloride, CO₂, calcium and phosphorous. Blood will be analyzed by a local laboratory.

^k = Women of childbearing potential must have a negative serum pregnancy test result ≤ 3 days prior to the first dose of rucaparib. A serum or urine pregnancy test (investigator's discretion) must be performed ≤ 3 days prior to Day 1 of every cycle during the treatment phase. A serum pregnancy test must be performed at the End of Treatment visit.

^l = includes dipstick for protein, glucose, blood, pH and ketones. If dipstick findings are abnormal based on investigator's assessment, microscopic evaluation should be performed.

^m = Disease assessment to include clinical examination, and appropriate imaging techniques, including CT scans of the chest, abdomen and pelvis, with appropriate slice thickness per RECIST; other studies (MRI, X-ray, PET, and ultrasound) may be performed if required. The same method used to detect lesions at baseline are to be used to follow the same lesions throughout the clinical study. If a patient has known brain metastases, this disease should be evaluated at each required assessment.

ⁿ = Tumor scans to be performed within 7 days prior to start of every odd numbered cycle, ie prior to start of Cycle 3, Cycle 5, Cycle 7, etc. A confirmatory scan should be performed ≥ 4 weeks after an initial response of PR or CR is observed.

^o = End of treatment CT scans should be performed if treatment was discontinued for reason other than radiologic disease progression.

^p = If CT scans were not performed at End of Treatment or within 28 days prior to End of Treatment, a CT scan should be performed at the 28-day follow-up visit.

^q = Archival tumor tissue, if available, will be collected and stored. (Note: This sample is not required to be submitted on Cycle 1, Day 1, but should be submitted as soon as possible after a patient begins treatment with rucaparib).

^r = A screening tumor biopsy will be collected if deemed safe and feasible. A biopsy will be collected if the reason for discontinuation was radiologic disease progression.

CONFIDENTIAL

^s= All patients discontinued from treatment, regardless of reason, should be followed for survival every 8 weeks until death, loss to follow-up, withdrawal of consent from study, or closure of the study. Follow-up can be performed via telephone.

^t= Up to 50cc of whole blood to be collected in 4 total tubes, likely to include EDTA and Streck tubes. Refer to laboratory manual for details. *If a patient has been on for >12 cycles, stop collecting serial ctDNA until progression or concern for progression.

^u= Patients will have coagulation tests PT/PTT/INR in advance of the clinical trial biopsy

^w= A biopsy will be obtained at progression if deemed safe and feasible. For patients some patients this will not be considered end of treatment as they may be permitted to remain on treatment past progression ^x= Following C11D1 of treatment, patients who are deemed to be clinically stable as per the investigator may have office visits and blood work at every odd cycle only. Subjects will be required to have monthly hematology labs (complete blood counts). A cycle will then be 56 days.

^y= Following C24D1 of treatment, patients who are deemed to be clinically stable as per the investigator may have office visits, including imaging and clinical assessments, Q12 weeks instead of Q8 weeks. A cycle will then be 84 days. Clinical labs should still be obtained once per month.

